16.0 Statistical Considerations and Methodology

16.1 Study Design: This phase I/II study involves three single arm phase I trials designed to determine the MTD and toxicity of lenalidomide in the treatment of multiple myeloma in three groups of patients defined by renal dysfunction. Once an MTD is determined within a group, an additional 15 patients will be accrued within the group and treated with the MTD as part of the phase II study to assess efficacy of lenalidomide and dexamethasone in the treatment of multiple myeloma. The 6 phase I patients treated at the MTD plus 15 additional patients accrued in each group will be combined (total = 63 patients) to assess efficacy using a one-stage design.

The first phase I study enrolls patients with moderate renal dysfunction (Group A); the second one enrolls patients with severe renal dysfunction (Group B); and the third one enrolls patients with ESRD renal dysfunction (Group C). Groups A, B, and C have a maximum of 3, 4, and 4 dose levels respectively. The MTD for each group will be determined concurrently.

16.11 Sample Size: **Phase I:** For Group A, the study may involve a maximum of 18 patients (6 for each of the 3 dose levels) but would likely require 15 patients (3 at the first dose level, 6 for the dose level prior to the MTD, and 6 at the MTD). For Group B, the study may involve a maximum of 24 patients (6 for each of the 4 dose levels) but would likely require 18 patients (3 at the first 2 dose levels, 6 for the dose level prior to the MTD, and 6 at the MTD). For Group C, the study may involve a maximum of 24 patients (6 for each of the 4 dose levels) but would likely require 18 patients (3 at the first 2 dose levels, 6 for the dose level prior to the MTD, and 6 at the MTD). **Phase II:** Each group will accrue an additional 15 patients at the MTD. **Overall:** Therefore, overall, the study needs a maximum of 111 patients, and an expected number of 96 patients.

In addition, the protocol allows replacement of patients in phase I who withdraw before completing cycle 1 for reasons other than toxicity.

16.12 MTD Determination: MTD is defined as the dose level below the lowest dose that induces dose-limiting toxicity in at least one-third of patients (at least 2 of a maximum of 6 new patients). MTD will be determined independently for each group as outlined in Section 7.2.

16.13 Accrual and Study Duration: We expect a 3-month period at the beginning of the study during which IRB approvals will be obtained. Then, given accrual history from PrECOG sites and assuming equal accrual to all three cohorts, it is estimated that 1.15 patients per week in each group will be accrued to this trial. Maximum total time per dose/group cohort of 6 patients will be:

2.5 weeks to enroll the first 3 patients
4 weeks to treat the first 3 patients through one cycle
1 week to assemble data and evaluate the outcome

2.5 weeks to enroll the second 3 patients
 4 weeks to evaluate their outcome
 1 week to assemble data and evaluate the outcome

This corresponds to a maximum requirement of approximately 15 weeks to enroll, treat, and evaluate 6 patients. Therefore, the accrual time for Groups A, B, and C will be 45 weeks, 60 weeks, and 60 weeks, respectively (note- these occur concurrently so the total duration of the phase I component is maximally 60 weeks with expected duration of 45 weeks) and the overall study duration will be 60 weeks (phase I component) + 15 weeks (accrual for 15 additional patients per group at 1 patient per group per week) + 24 weeks (6 cycles to treat and evaluate patients in the phase II component) = 99 weeks (about 23 months).

16.14 Operating Characteristics: The following table gives the probability of dose escalation at a single dose level as a function of the true probability of DLT at that level using the cohorts of 3 design described in Section 7.2.

True Rate of DLT (%)	Probability of Dose Escalation
10	0.91
20	0.71
30	0.49
40	0.31
50	0.17

16.2 Phase I Analysis Plans: Data will be analyzed separately within the three patient groups with the exception of the additional 15 patients per group accrued at the MTD (e.g., patients included in the phase II component). However, the analysis procedures, described below, are the same for the three groups. All the relevant phase I results pertaining to toxicity, MTD, response, timed endpoints and laboratory correlates will be examined in an exploratory and hypothesis-generating fashion.

16.21 Adverse Events Profile

The number and severity of all adverse events (overall and by dose-level) will be tabulated and summarized within the three patient groups. The grade 3+ adverse events will also be described and summarized in a similar fashion. This will provide an indication of the level of tolerance for this treatment combination in the three patient groups.

16.22 Toxicity Profile

As per NCI CTCAE V4.0, the term “toxicity” is defined as adverse events that are classified as either possibly, probably, or definitely related to study treatment. Non-hematologic toxicities will be evaluated via the ordinal CTCAE standard toxicity grading. Hematologic toxicity measures of thrombocytopenia, neutropenia, and leukopenia will be

assessed using continuous variables as the outcome measures (primarily nadir) as well as categorization via CTCAE standard toxicity grading.

Overall toxicity incidence as well as toxicity profiles by dose level will be explored and summarized. Frequency distributions, graphical techniques and other descriptive measures will form the basis of these analyses.

Further, the overall toxicity profiles and the MTD will be compared in an exploratory fashion among the three groups for any possible differences.

Lastly, the duration of treatment, dose level and total dose per agent each cycle will be summarized using descriptive statistics overall per group and by dose level per group.

16.23 Timed Endpoints

The data on time-related variables will be summarized descriptively. These include time until any treatment related toxicity, time until treatment related grade 3+ toxicity, time until hematologic nadirs (WBC, ANC, platelets), time to progression and time to treatment failure, where time to treatment failure is defined as the time from registration to documentation of progression, unacceptable toxicity, or refusal to continue participation by the patient.

16.3 Phase II Design and Analysis

16.3.1 Primary Endpoint and Estimation:

The primary endpoint is the proportion of patients who have at least a partial response to treatment. Throughout Section 16.3, partial response or better will be considered synonymous with “success”, unless specified otherwise. The 6 patients treated at the recommended dose level (MTD) within each group will be included in the analysis for this portion of the study. The efficacy population will include the 63 patients across groups and include all patients meeting eligibility criteria who signed a consent form and began treatment.

The proportion of successes will be estimated by the number of successes divided by the total number of patients in the efficacy population. Eligible, treated patients who are unevaluable for response will be included in the denominator when estimating the proportion of successes. Confidence intervals for the true success proportion will be calculated according to the properties of the binomial distribution. Secondary analyses include estimation of the proportion of successes with confidence intervals for each group.

16.3.2 Statistical Design:

The largest success proportion where the proposed treatment regimen would be considered ineffective in this population is 40%, and the smallest success proportion that would warrant subsequent studies with the proposed regimen in this patient population is 55%. The following one-stage design based on the binomial distribution uses 63 patients to test the null hypothesis that the true success proportion in a given patient population is at most 40%.

The success rate of 40% is based on the results of two phase III studies of lenalidomide plus dexamethasone versus dexamethasone alone in relapsed or refractory multiple myeloma (MM-009, North America, 353 patients; MM-010, Europe, Australia, and Israel, 351 patients). The overall response (\geq PR) rates associated with lenalidomide and dexamethasone were 61% and 59.1% in MM-009 and MM-010, respectively, and the overall response rates associated with dexamethasone (plus placebo) were 20.5% and 24% in MM-009 and MM-010, respectively, with a median follow-up of 17.1 months (MM-009) and 16.5 months (MM-010) as reported by Weber et al¹⁹. An additional pooled subgroup analysis was reported by Weber et al¹⁹ investigating renal dysfunction groups. Overall response rate to lenalidomide and dexamethasone was not significantly different between patients with creatinine clearance above 60 ml/min and patients with creatinine clearance below 60 ml/min. However, for 16 patients with creatinine clearance below 30 ml/min, median time to progression and overall survival were significantly shorter than for those with creatinine clearance above 30 ml/min. Further, the median time to progression and overall survival of patients with creatinine clearance below 30 ml/min was significantly greater than patients with creatinine clearance below 30 ml/min on the dexamethasone (and placebo) arm. Results for overall response rate in the <30 ml/min group were not reported. Based on this, it is reasonable to anticipate that the overall response rate in (at least) Group B and Group C of the current study will be less than 60%. However, the study chairs felt that an overall response rate of 40% would be the minimum acceptable in this context.

16.33 Decision Rule: Enter 63 patients into the study. If 30 or fewer successes are observed in 63 eligible, treated patients, we will consider this regimen ineffective in this patient population and terminate this study. If 31 or more successes are observed among 63 eligible, treated patients, we may recommend further testing of this regimen in subsequent studies in this population.

16.34 Over Accrual: If more than the target number of patients are accrued, the additional patients will not be used to evaluate the stopping rule or used in any decision making process but will be included in all final point estimates.

16.35 Power and Significance Level: Assuming that the number of successes is binomially distributed, the significance level is \geq 10% and the probability of declaring that this regimen warrants further studies (e.g., statistical power) under various success proportions can be tabulated as a function of the true success proportion as shown in the following table.

If the true success proportion is	0.4	0.45	0.5	0.55	0.6
then the probability of declaring that the regimen warrants further studies is	0.09	0.29	0.60	0.85	0.97

16.36 Analysis Plan: The analysis for this trial will commence at planned time points and at the time the patients have become evaluable for the primary endpoint. Such a decision will be made by the Statistician and Study Chair, in accord with PrECOG Standard Operating Procedures, availability of data for secondary endpoints (e.g., laboratory correlates), and

the level of data maturity. It is anticipated that the earliest date in which the results will be made available via manuscript, abstract, or presentation format is 24 months.

16.37 Definitions and Analyses of Secondary Endpoints:

Survival time is defined as the time from registration to death due to any cause. The distribution of survival time will be estimated using the method of Kaplan-Meier.

Progression-free survival time is defined as the time from registration to the earliest date of documentation of disease progression. If a patient dies without a documentation of disease progression the patient will be considered to have had disease progression at the time of their death. If the patient is declared to be a major treatment violation, the patient will be censored on the date the treatment violation was declared to have occurred. In the case of a patient starting treatment and then never returning for any evaluations, the patient will be censored for progression on day 1 post-registration. The distribution of progression-free survival time will be estimated using the method of Kaplan-Meier.

Duration of response is defined for all eligible, treated patients who have achieved a partial response or better as the date at which the patient's earliest objective status is first noted to be either a partial response or better to the earliest date progression is documented.

Time to treatment failure is defined to be the time from registration to the date at which the patient is removed from treatment due to progression, adverse events, or refusal. If the patient is considered to be a major treatment violation or is taken off study as a non-protocol failure, the patient will be censored on the date they are removed from treatment.

Adverse Events: All eligible patients who began treatment will be considered evaluable for assessing adverse event rate(s). The maximum grade for each type of adverse event will be recorded for each patient, and frequency tables will be reviewed to determine patterns. Additionally, the relationship of the adverse event(s) to the study treatment will be taken into consideration. The duration of treatment, dose level and total dose per agent each cycle will also be summarized using descriptive statistics. Lastly, renal function over time will be described using descriptive statistics.

16.38 Pharmacokinetic Analysis:

Pharmacokinetic (PK) analysis will be performed in consented subjects administered a dose during the "Phase II" portion of the trial.

The following pharmacokinetic parameters will be determined using the non-compartmental methods:

- Maximum observed plasma concentration (C_{\max})
- Time to maximum plasma concentration (t_{\max})
- Area under the plasma concentration-time curve from Time 0 to the last measurable time point (AUC)

- Area under the plasma concentration-time curve from Time 0 to infinity (AUC_{∞})
- Apparent total body clearance when dosed orally (CL/F)
- Apparent volume of distribution when dosed orally (V_z/F)
- Terminal elimination half-life in plasma ($t_{1/2,z}$)

The relationship between renal function (CrCl) and PK parameters will be explored.

The results will be summarized by descriptive statistics.

16.4 Data & Safety Monitoring:

Study Monitoring: PrECOG, LLC will be responsible for study monitoring. Refer to Section 19.5 for details.

Adverse Event Stopping Rule: The stopping rule specified below is based on the knowledge available at study development. We note that the Adverse Event Stopping Rule may be adjusted in the event of either (1) the study re-opening to accrual or (2) at any time during the conduct of the trial and in consideration of newly acquired information regarding the adverse event profile of the treatment(s) under investigation. The study team may choose to suspend accrual because of unexpected adverse event profiles that have not crossed the specified rule below.

Accrual will be temporarily suspended to a group if at any time we observe events considered at least possibly related to study treatment (e.g., an adverse event with attribute specified as “possible”, “probable”, or “definite”) that satisfy the following:

- If 7 or more patients in the first 20 treated patients (or 33% of patients after 20 have been accrued) experience a grade 4 or higher non-hematologic adverse event.

We note that we will review grade 4 and 5 adverse events deemed “unrelated” or “unlikely to be related”, to verify their attribution and to monitor the emergence of a previously unrecognized treatment-related adverse event. The adverse event rule will be evaluated for each group using all patients in the group who initiate treatment (e.g., will include patients in the phase I and phase II components).

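### Protocol 16.35 states a significance level of 10% or more although the 31-of-63 rule gives 0.087, and 16.33 has no rule for fewer than 63 eligible, treated patients

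*Protocol*

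**What the plan says.** Protocol 16.3.2 sets a one-stage binomial design that "uses 63 patients to test the null hypothesis that the true success proportion in a given patient population is at most 40" per cent. The smallest response rate of interest is 55%.

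Protocol 16.33 begins "Enter 63 patients into the study". It then gives the rule: "If 30 or fewer successes are observed in 63 eligible, treated patients", the regimen is judged ineffective; with 31 or more it may go forward. Both halves of the rule use 63 eligible, treated patients as the denominator.

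Protocol 16.35 reads "Assuming that the number of successes is binomially distributed, the significance level is", followed by a greater-than-or-equal sign and 10%. The table row beneath it, "then the probability of declaring that the regimen warrants further studies is", lists 0.09, 0.29, 0.60, 0.85 and 0.97 for true response rates of 0.40, 0.45, 0.50, 0.55 and 0.60.

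These provisions bear on the denominator:
- Protocol 16.1 builds the 63 as 6 phase I patients at the MTD plus 15 more in each of three groups.
- Protocol 16.3.1 limits the efficacy population to eligible, consented patients who began treatment. Eligible, treated patients who are unevaluable stay in the denominator.
- Protocol 13.1 and 13.3 provide for patients found ineligible after registration and for patients cancelled before any treatment.
- Protocol 13.6 and 16.11 describe replacement for phase I patients who leave before completing cycle 1 for reasons other than toxicity.
- Protocol 16.34 keeps patients beyond the target out of the decision.
- The SAP repeats the sample size (8.1) and defines efficacy patients by eligibility and treatment (8.5.3), but contains no decision rule.

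**The concern.** There are two separate matters. The first is that a level of 10% or more puts no ceiling on the false-positive rate, and it disagrees with the table directly below it. Someone who quotes the sentence and not the table would report the wrong design error rate.

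The second is that the number to be entered and the number on which the decision rests are both 63. They coincide only if no entered patient is later found ineligible or goes untreated, and Section 13 foresees both outcomes. Protocol 16.33 gives one cut-off for one denominator. If the final efficacy set were, say, 60, someone would have to choose a threshold after the data are in, in an open single-arm trial where responses are already known. Keeping 31 by default would make the rule stricter than tabulated and would cost power.

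**Working it through.** **Inputs.** Null rate 0.40 and alternative 0.55 (Protocol 16.3.2); n = 63 and cut-off 31 (16.33); tabulated probabilities (16.35).

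**Step 1: reproduce the table.** With X binomial(63, p), as the protocol assumes,

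P(X ≥ 31) = Σ (k = 31 to 63) C(63, k) p^k (1 − p)^(63 − k).

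| True rate p | Protocol 16.35 | Exact |
|---|---|---|
| 0.40 | 0.09 | 0.0873 |
| 0.45 | 0.29 | 0.2922 |
| 0.50 | 0.60 | 0.5993 |
| 0.55 | 0.85 | 0.8533 |
| 0.60 | 0.97 | 0.9687 |

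All five entries agree to two decimals.

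**Step 2: could a different cut-off explain a level of 10% or more?** A cut-off of 30 gives level 0.1347 and power 0.9036. A cut-off of 32 gives 0.0537 and 0.7878. Neither matches the table. The rule and table belong together, and the inequality in the sentence is the part that does not fit.

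**Step 3: where the 63 comes from.** (6 + 15) × 3 = 63, or 21 per group. There is no allowance for losses.

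**Step 4: smaller efficacy sets.** The documents give no rate of ineligible or untreated patients. I assume 1 to 5 lost, which is 1/63 = 1.6% to 5/63 = 7.9%. The middle columns keep 31. The right-hand columns use the smallest cut-off with level at most 0.10.

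| Eligible, treated n | Level, cut-off 31 | Power at 0.55, cut-off 31 | Re-derived cut-off | Level | Power at 0.55 |
|---|---|---|---|---|---|
| 63 | 0.0873 | 0.8533 | 31 | 0.0873 | 0.8533 |
| 62 | 0.0708 | 0.8211 | 31 | 0.0708 | 0.8211 |
| 61 | 0.0565 | 0.7841 | 30 | 0.0921 | 0.8513 |
| 60 | 0.0445 | 0.7424 | 30 | 0.0746 | 0.8183 |
| 59 | 0.0344 | 0.6960 | 29 | 0.0972 | 0.8493 |
| 58 | 0.0262 | 0.6454 | 29 | 0.0787 | 0.8154 |

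With 31 kept, power falls from 0.85 to between 0.82 and 0.65. With the cut-off re-derived, the largest loss in this range is 0.8533 − 0.8154 = 0.038, about 4 points. At n = 62 the two approaches give the same cut-off, so one lost patient costs about 3 points either way.

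**The case against.** **On the sign.** The true level stands in the table immediately below the sentence, and no decision changes. The sign may come from the conversion of the PDF, although other inequalities in the supplied text, such as those in the eligibility criteria, read correctly. This stands: the point is editorial, and the source page should be checked first. A reader might infer from the sentence that the trial runs at a false-positive rate of 10% or more. The cut-off and the table show that it does not.

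**On the denominator.** Protocol 16.33 names 63 eligible, treated patients twice, 16.3.1 describes the efficacy population as the 63 across groups, and the 2015 SAP amendment speaks of 63 treated at the MTD. Read together, these can mean that 63 is the number to be reached after losses, in which case the power of 0.85 stands as printed. A reader might nevertheless infer that 0.85 is overstated, that phase II replacement is ruled out, or that about 11 points of power are lost (0.8533 − 0.7424 at n = 60). The documents do not support these inferences. They are silent on making up losses in phase II, which is not a prohibition. They never say to keep 31 with fewer than 63. They give no loss rate. The usual source of shrinkage, unevaluable patients, is already handled because those patients remain in the denominator.

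What remains is an ambiguity. The instruction to enter 63 and the fixed 15 additional patients per group do not say that losses are made up. If the target in 16.34 means 63 entered, a make-up patient would count as over-accrual and be left out of the decision.

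**Conclusion.** The sentence in 16.35 is wrong as supplied: the one-sided level of the 31-of-63 rule is 0.087, below 10%, subject to a check of the sign in the source PDF. The cut-off, the sample size and the power table are correct and need no change.

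The decision rule is incomplete, not miscalculated. It is defined for exactly 63 eligible, treated patients and says nothing about a smaller number, although the protocol foresees how one could arise. The power range of 0.82 down to 0.65, with level 0.071 down to 0.026, depends on two assumptions that the documents do not make: 1 to 5 patients lost, and 31 kept as the cut-off. If losses are made up, none of it applies. Severity is minor.

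**What to change.** 1. In 16.35, check the sign against the source and state: one-sided significance level below 10% (exact 0.087). This costs one corrected phrase.

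2. In 16.33, choose one of the following before the response data are analysed:
   - State that accrual continues until 63 eligible, treated patients, 21 per group, are reached, and that the target in 16.34 is this number. The tabulated level and power then stand. The cost is a few extra registrations if patients are lost.
   - Pre-specify the cut-off for smaller efficacy sets, in the protocol or as a note to the SAP: 62 patients, 31 (level 0.071, power 0.82); 61, 30 (0.092, 0.85); 60, 30 (0.075, 0.82); 59, 29 (0.097, 0.85); 58, 29 (0.079, 0.82). This needs a five-line table and no extra patients, and accepts up to about 4 points less power at some sizes.

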9. All patients must be counseled about pregnancy precautions, risks of fetal exposure and other risks. The counseling must be done on Day 1 of each cycle (or at a minimum of every 28 days) throughout the entire duration of lenalidomide treatment, including dose interruptions, and at lenalidomide discontinuation. The Appendix VI: Education and Counseling Guidance Document must be completed by a trained Counselor (Counselors will be trained by Celgene).
10. Only enough lenalidomide for 1 cycle of therapy may be provided to the patient each cycle.
11. Refer to Section 10.2 for minimum events to be collected at baseline and each evaluation.
12. Except Day 1 of Cycle 1.
13. On Day 1 of each cycle, the ANC must be $\geq 1,000/\mu\text{L}$ and the platelet count must be $\geq 50,000/\mu\text{L}$.
14. Serum creatinine only.
15. Bone marrow aspirate and biopsy are **only** required to document or confirm CR or sCR, except for patients with evaluable disease **only**, where a bone marrow is required to document all response categories including progression (see Section 11.3). However, a second confirmatory bone marrow is **not** required to confirm response.
16. An additional safety assessment will be done 30 days (+/- 2 days) following the last dose of study drug.
17. Therapy may be interrupted to allow for stem cell harvest and mobilization for patients treated beyond 4 cycles.
18. Follow-up every 6 months for survival, second primary malignancy diagnosis, and recurrence of any prior malignancy (if applicable) x 3 years. If patient has not progressed at off-study, document date of progression. This should include subjects who may have discontinued the study at any time or for any reason, who may be in a survival follow-up period, or who may have died. Following this 3 year time period, reporting of all identified cases of subsequently diagnosed second primary malignancies is voluntary by the treating physician to the manufacturer.
19. Note: In addition to the standard evaluation for prolonged cytopenias that do not recover after discontinuation of treatment, a bone marrow exam should be considered, in patients with the following parameters: no leukopenia at the time of multiple myeloma diagnosis, no active multiple myeloma at the time of the cytopenia, no vitamin or element deficiency to explain the cause of the cytopenia(s).

R Research test. Will be charged to study and not to patient's account.

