13.0 Treatment/Follow-Up Decision at Evaluation of Patient

13.1 If it is determined that after registration a patient did not satisfy each and every eligibility criteria, the patient will be noted as being *ineligible*. The patient may continue treatment off-protocol at the discretion of the physician as long as there are no safety concerns, and the patient was properly registered. The patient will go directly to the follow-up/event monitoring phase of the study.

- If the patient received treatment, all data up until the point of confirmation of ineligibility must be submitted. Follow-up per Section 4.0 and event monitoring per eCRF completion guidelines will be required.
- If the patient never received treatment, on-study material must be submitted. Follow-up per Section 4.0 and event monitoring per eCRF completion guidelines will be required.

13.2 If a required treatment/procedure in cycle 1 is not done and the violation is deemed severe, the patient will be noted as having a *major violation*. All data up until the point of confirmation of a major violation must be submitted. The patient will go directly to follow-up/event-monitoring phase of the study. The patient may continue treatment off-protocol at the discretion of the physician as long as there are no safety concerns, and the patient was properly registered. Follow-up per Section 4.0 and event monitoring per eCRF completion guidelines will be required.

13.3 If a patient is removed from the study for any reason before any study treatment is given, the patient will be noted as having been *cancelled*. On-study material and the End of Active Treatment/Cancel Notification Form must be submitted. No further data submission is necessary.

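### PFS censors cycle 1 major violators although their later progression and death are to be collected, and the day-1 rule for patients who never return has no exception for death

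*Protocol*

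**What the plan says.** Protocol 16.37 measures PFS from registration to the first documentation of progression. It then gives three rules in sequence:

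- Death without documented progression: "the patient will be considered to have had disease progression at the time of their death".
- Major treatment violation: "the patient will be censored on the date the treatment violation was declared to have occurred".
- Treatment started but no return for any evaluation: "the patient will be censored for progression on day 1 post-registration".

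No order of precedence is given. The estimator is Kaplan-Meier: "The distribution of progression-free survival time will be estimated using the method of Kaplan-Meier". SAP 8.4.2 repeats all three rules, SAP 9 declares no changes from the protocol analyses, and neither document plans a sensitivity analysis without the two censoring rules.

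Protocol 13.2 says when a violation is major: "If a required treatment/procedure in cycle 1 is not done and the violation is deemed severe". Such a patient leaves protocol treatment for the follow-up and event-monitoring phase, and "Follow-up per Section 4.0 and event monitoring per eCRF completion guidelines will be required". Footnote 18 to the Test Schedule sets that follow-up: "Follow-up every 6 months for survival, second primary malignancy diagnosis, and recurrence of any prior malignancy (if applicable) x 3 years". It adds: "If patient has not progressed at off-study, document date of progression", and it covers patients who discontinued at any time and for any reason.

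**The concern.** Two separate problems arise.

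**Violators.** The trial collects dates of progression and death for these patients and then leaves them out of PFS. Because a major violation is a cycle 1 event, censoring falls within roughly the first 28 days, so almost all of the patient's PFS experience is lost. The same eligible, treated patient stays in the response denominator (Protocol 16.3, SAP 8.6.1) and in overall survival, which has no violation rule. Kaplan-Meier assumes that censored patients have the same later risk as those who remain. If patients whose required treatment or procedure was not done in cycle 1 are at higher risk, the curve is too high.

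**Patients who never return.** A treated patient who dies before any evaluation fits both the death rule and the day-1 rule. Two programmers could code this patient in opposite ways and each cite the text. Under the day-1 rule, one early death would be a survival event, a response failure and a censored PFS time.

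PFS is a named secondary objective, and its reported value should not depend on an unstated precedence.

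**Working it through.** **Plan's own figure.** The documents state no PFS median, rate or event count, so there is nothing to reproduce for PFS. The nearby design table in Protocol 16.35 does reproduce. With 63 patients and success at 31 or more, the exact binomial tail is 0.0873, 0.2922, 0.5993, 0.8533 and 0.9687 at true response rates 0.40, 0.45, 0.50, 0.55 and 0.60, against the stated 0.09, 0.29, 0.60, 0.85 and 0.97. That calculation does not use PFS.

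**Which rule applies to which patient**

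| Patient | Death rule | Violation rule | Day-1 rule | Result as written |
|---|---|---|---|---|
| Violator, later progresses | – | censor at violation | – | recorded event discarded |
| Violator, later dies without progression | event at death | censor at violation | – | no precedence stated; the earlier date is the censoring |
| Treated, never returns, known to have died | event at death | – | censor on day 1 | conflict |
| Treated, never returns, no known death | – | – | censor on day 1 | no conflict |

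**Size, violators (illustration).** Assumed inputs: exponential PFS with median m of 6, 9 or 12 months in other patients, λ = ln 2/m; k = 3 or 6 violators of 63, v = k/63; violators' hazard h times that of the others; censoring at t₀ = 28/30.4 = 0.92 months.

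- True curve: S(t) = (1−v)·exp(−λt) + v·exp(−hλt).
- Kaplan-Meier target with violators censored, for t > t₀: K(t) = S(t₀)·exp(−λ(t−t₀)).

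Example with m = 9, k = 6, h = 2: λ = 0.0770, v = 0.0952, S(t₀) = 0.9254. Solving K(t) = 0.5 gives 0.92 + ln(0.9254/0.5)/0.0770 = 8.92 months; solving S(t) = 0.5 gives 8.40.

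Each cell gives the true median, then the estimated median, in months:

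| m | k=3, h=2 | k=3, h=3 | k=6, h=2 | k=6, h=3 |
|---|---|---|---|---|
| 6 | 5.80, 5.96 | 5.69, 5.92 | 5.60, 5.92 | 5.39, 5.84 |
| 9 | 8.69, 8.96 | 8.54, 8.92 | 8.40, 8.92 | 8.09, 8.84 |
| 12 | 11.59, 11.96 | 11.39, 11.92 | 11.20, 11.91 | 10.78, 11.83 |

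The overstatement runs from 0.16 months (5.96 − 5.80) to 1.05 months (11.83 − 10.78). At h = 1 the two medians agree in every case.

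**Size, early deaths (illustration).** If k of 63 die before any evaluation and the rest are followed to the landmark, counting the deaths as events gives (63−k)/63 times the PFS of the others. Day-1 censoring drops the factor, so PFS is multiplied by 63/(63−k):

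- k = 3: 63/60 = 1.05, so a true 57.1% is shown as 60%.
- k = 6: 63/57 = 1.105, so a true 54.3% is shown as 60%.
- One such patient in a renal group of 6 + 15 = 21: 21/20 = 1.05.

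The median with the deaths counted is −ln(0.5/(1−k/63))/λ. For k = 1, 3 and 6 this gives 5.86, 5.58 and 5.13 months (m = 6); 8.79, 8.37 and 7.70 (m = 9); 11.72, 11.16 and 10.27 (m = 12). Day-1 censoring would show 6, 9 and 12.

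**The case against.** The best defence of the early-death handling is the text itself. The death sentence comes first and carries no exception, and the day-1 rule reads naturally as one for loss to follow-up. A reader might infer that the plan will censor early deaths. The documents do not support that; they support only that the two sentences conflict and that either coding can be defended. Cycle 1 also has visits on days 8, 15 and 22, and entry requires performance status 0 to 2 without uncontrolled illness, so deaths before any evaluation may be few. Nothing in the documents supports 3 to 6 of them.

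A reader might also take the violation rule to censor at the date of declaration, which could drift with outcome in an open-label trial. The wording more naturally means the date of the violation itself, and 13.2 ties that to cycle 1. Whether a violation is severe remains a judgement without stated criteria, but the date is not free to move.

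Nor do the documents show that violators have a worse prognosis: a missed procedure may be a site error. Violators may continue treatment off protocol, so censoring them is a recognisable, if less preferred, way to describe PFS under protocol treatment. The different handling in the response analysis is not an error in itself, since counting unevaluable patients as non-responders and censoring them in a time-to-event analysis are both ordinary conventions.

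Finally, the Follow-Up column of the Test Schedule lists no SPEP, UPEP or free light chains. Progression after a violation would be found on a sparser schedule, possibly late. This limits what the change gains but does not justify discarding a recorded event.

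**Conclusion.** The point stands, in limited form. The violator part is firm as a matter of text: follow-up for progression and death is required, and PFS ignores what it yields. Its effect is upward only if violators carry higher risk; at equal risk it is nil. The size is unknown, and the 0.16 to 1.05 months above rests on assumed counts, hazards and medians. The early-death part is a conflict between two sentences; the factor 63/(63−k) applies only if the conflict is resolved in favour of day-1 censoring, with k assumed.

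A firm statement that reported PFS is biased upward would go beyond the documents. PFS here is a secondary, single-arm, descriptive estimate with no test or threshold. Early deaths still appear in overall survival, and the rule of 31 successes among 63 is unaffected. This is a cheap improvement rather than a threat to the trial's main conclusion.

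**What to change.** In Protocol 16.37 and SAP 8.4.2:

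1. State that any known death or documented progression is a PFS event and takes precedence over day-1 censoring.
2. Limit day-1 censoring to patients with no evaluation and no known death.
3. In the main PFS analysis, follow major violators to progression or death, using the dates collected under 13.2 and footnote 18.
4. Report PFS with violators censored as a sensitivity analysis, and say that the censoring date there is the date on which the violation occurred, if that is what is meant.
5. Record the change in SAP 9.

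The cost is wording and one extra analysis; the follow-up it relies on is already required. Reported PFS may be slightly lower. Because progression after a violation is ascertained on the sparser follow-up schedule, some progression dates may be late, and the report should say so.
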